**Table 3: Guidelines for Management of Treatment Emergent Hepatotoxicity**

Event	Dose Modification Algorithms
(A). ALT of $\leq 3.0 \times$ ULN	Continue Pazopanib at current dose with full panel LFT (a) monitored as per protocol.
(B). ALT $>3.0 \times$ ULN to $\leq 8.0 \times$ ULN without bilirubin elevation (defined as total bilirubin (b) $<2.0 \times$ ULN or direct bilirubin $\leq 35\%$ ) and without hypersensitivity symptoms (e.g., fever, rash)	
Liver Event Monitoring Criteria:
 
(1) Continue Pazopanib at current dose levels.
 
(2) Monitor subject closely for clinical signs and symptoms; perform full panel LFTsa weekly or more frequently if clinically indicated until ALT/AST is reduced to Grade 1.

(C). ALT $>8.0 \times$ ULN without bilirubin elevation (defined as total bilirubin b $<2.0 \times$ ULN or direct bilirubin $\leq 35\%$ ) and without hypersensitivity symptoms (e.g., fever, rash)	
1st occurrence – Liver Event Interruption Criteria:
 
(1) Interrupt Pazopanib until toxicity resolves to <math>\leq</math> Grade 1 or baseline. Report the event to Sponsor as an SAE within 24 hours of learning of its occurrence. Make every reasonable attempt to have subjects return to the clinic within 24 to 72 hours for repeat liver chemistries and liver event follow up assessments.
 
(2) Liver imaging and other laboratory investigations should be considered as clinically appropriate.
 
(3) Monitor subject closely for clinical signs and symptoms; perform full panel LFTsa weekly or more frequently if clinically indicated until ALT/AST is reduced to Grade 1.
 
(4) If the subject is benefiting from the study treatment, contact Study Chief Physician for possible re-challenge. Re-treatment may be considered if ALL following criteria are met:
 
 
- ALT/AST reduced to Grade 1
 
- Total bilirubin <math><1.5 \times</math> ULN or direct bilirubin <math>\leq 35\%</math>
 
- No hypersensitivity signs or symptoms
 
- Subject is benefiting from therapy.
 
 
(5) Reintroduce Pazopanib, if warranted, at lower dose.
 
Recurrence – Liver Event Stopping Criteria:
 
If aminotransferase levels <math>> 3 \times</math>ULN recur, discontinue Pazopanib permanently and monitor subject closely for clinical signs and symptoms; perform full panel LFTsa weekly or more frequently if clinically indicated until ALT/AST is reduced to Grade 1.

(D). ALT $>3.0 \times$ ULN with concomitant elevation in bilirubin (b) (defined as total bilirubin $\geq 2.0 \times$ ULN; with direct bilirubin $>35\%$ ) or with hypersensitivity symptoms (e.g., fever, rash).	
Liver Event Stopping Criteria:
 
(1) Discontinue Pazopanib immediately, report the event to Sponsor as an SAE within 24 hours of learning of its occurrence. Make every reasonable attempt to have subjects return to the clinic within 24 hours for repeat liver chemistries and liver event follow up assessments.
 
(2) Consult a gastroenterologist / hepatologist, and perform the following assessments to identify potential co-factors:
 
 
- Eosinophil count
 
- Viral serology for hepatitis A, B, C and E, cytomegalovirus, Epstein-Barr virus (IgM antibody, heterophile antibody, or monospot testing)
 
- Anti-nuclear antibody, anti-smooth muscle antibody, Type 1 anti-liver kidney microsomal antibodies.
 
- Serum creatinine phosphokinase for possible muscle injury caused LFT elevation
 
- Liver imaging
 
- Consider toxicological blood screen for possible contributing chemical/medical entities
 
 
(3) Monitor subject closely for clinical signs and symptoms; record the appearance or

	worsening of clinical symptoms of hepatitis, or hypersensitivity, such as fatigue, nausea, vomiting, right upper quadrant pain or tenderness, fever rash or eosinophilia as relevant on the AE report form. Perform full panel LFTs a weekly or more frequently if clinically indicated until LFTs are reduced to Grade 1.
For isolated total bilirubin(b) elevation without concurrent ALT increases (defined as ALT <3 X ULN).	(1) Isolated hyperbilirubinemia (i.e., in the absence of elevated ALT or other signs/symptoms of liver injury) does not require dose modification. Pazopanib inhibits UGT1A1 and OATP1B1, which can cause elevation of indirect (unconjugated) bilirubin in the absence of liver injury. (2) If bilirubin is >1.5 x ULN in the absence of ALT elevation, fractionation of bilirubin elevation should be performed. If bilirubin is >35% direct (conjugated), further evaluation for underlying cause of cholestasis should be performed.

(a) Full panel LFTs include: AST, ALT, alkaline phosphatase, GGT, and total bilirubin. Coagulation tests should be performed as clinically indicated.

(b) Serum bilirubin fractionation should be performed if testing is available. If testing is unavailable and a subject meets the criterion of total bilirubin >1.5 x ULN, then the event should be promptly reported as an SAE.

**Abbreviations:** **ALT** alanine aminotransferase; **AST** aspartate aminotransferase; **eCRF** electronic case report form; **IP** investigational product; **LFT** liver function tests; **SAE** serious adverse event; **ULN** upper limit of normal

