**Additionally, for the purpose of this study it will be considered as SAEs, all hepatotoxicities as follows:**

**1) ALT >3.0 x ULN with concomitant elevation in bilirubin (defined as total bilirubin  $\geq$  2.0 x ULN, with direct bilirubin >35%) or with hypersensitivity symptoms (e.g., fever, rash) – bilirubin fractionation should be performed if testing available**

**2) ALT >8.0 x ULN without bilirubin elevation (defined as total bilirubin <2.0 x ULN or direct bilirubin  $\leq$  35%) and without hypersensitivity symptoms (e.g., fever, rash) – bilirubin fractionation should be performed if testing available**

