**Table 6: Clinical Laboratory Assessments**

Clinical Chemistry	
Renal function	Urea, Creatinine
Liver function test (LFT) Panel	Albumin, Alkaline phosphatase, Alanine aminotransferase (ALT), Aspartate aminotransferase (AST) and Bilirubin (total) b
Electrolytes and others	Calcium, Potassium, Sodium, Magnesium, Inorganic phosphate, Glucose, and Lactate Dehydrogenase (LDH)
Hematology	Hematocrit, Hemoglobin, White Blood Cell Count, Red Blood Cell Count, Neutrophils, and Platelets
Coagulation Tests	Activated partial thromboplastin (aPTT) and International Normalization Ratio (INR) c
Urinalysis for Proteinuria	UPC d
Thyroid Function Test	TSH e

a) Estimated creatinine clearance should be calculated using the Cockcroft and Gault method (Annex III). Alternatively, creatinine clearance can be measured directly by 24-hour urine collection.

b) A direct bilirubin level should be obtained if the total bilirubin level is greater than 1.5 X upper limit of normal (ULN). See Section 7.6.2 for stopping criteria and dose modification guidelines for treatment-emergent liver function abnormality.

c) Coagulation tests may also be performed in response to an AE/SAE of bleeding and as clinically indicated.

d) UPC should be evaluated as described in Annex II or by 24-hour urine protein. If UPC  $\geq$  3 or if urine protein is  $\geq$  3g, then the dose modification table guidelines should be followed (Section 7.6.1).

e) Unscheduled thyroid function tests [TSH and thyroxine (free T4)] should be performed if clinically indicated (e.g., if a subject develops signs and symptoms suggestive of hypothyroidism).

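### With ALT >3 x ULN, total bilirubin >=2.0 x ULN, no hypersensitivity symptoms and an unknown direct fraction, Table 3 cannot assign a row, and its fallback SAE rule does not match sections 9.1 and 9.2

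*Protocol*

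**What the plan says.** Protocol 7.6.2, Table 3, sorts patients with ALT above 3 x ULN as follows:

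- **Row B** (ALT >3 to 8 x ULN) requires total bilirubin <2.0 x ULN or direct bilirubin <=35%, and no hypersensitivity symptoms. The action is "Continue Pazopanib at current dose levels".
- **Row C** (ALT >8 x ULN) has the same bilirubin and hypersensitivity conditions. The action is to interrupt, with possible re-challenge, and to report an SAE.
- **Row D** (ALT >3 x ULN) requires total bilirubin >=2.0 x ULN with direct >35%, or hypersensitivity symptoms. The action is "Discontinue Pazopanib immediately, report the event to Sponsor as an SAE".
- **Isolated-bilirubin row** (ALT <3 x ULN): "Isolated hyperbilirubinemia (i.e., in the absence of elevated ALT or other signs/symptoms of liver injury) does not require dose modification". Above 1.5 x ULN, fractionation is requested.

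Footnote (b) is marked on the bilirubin term of rows B, C and D and of the isolated-bilirubin row. It asks for fractionation where the test is available. It then adds a fallback: "If testing is unavailable and a subject meets the criterion of total bilirubin >1.5 x ULN", the event is to be reported promptly as an SAE.

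Sections 9.1 and 9.2 list two study-specific liver SAEs. The first begins "ALT >3.0 x ULN with concomitant elevation in bilirubin (defined as total bilirubin" and sets the limit at >=2.0 x ULN with direct >35%, or hypersensitivity symptoms. The second is ALT >8 x ULN without that bilirubin elevation and without hypersensitivity symptoms. Both ask for fractionation only if available.

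Annex III, Table 6, footnote b has no such condition: "A direct bilirubin level should be obtained if the total bilirubin level is greater than 1.5 X upper limit of normal (ULN").

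**The concern.** Combined elevation of ALT and bilirubin is what row D is there to act on. In part of that range the table needs a result that three places in the protocol treat as possibly unavailable. Footnote (b) foresees the missing result but covers reporting only. Two investigators with the same patient could then follow opposite dose instructions, each with a row to point to.

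Reporting has a related problem. Staff working from section 9 and staff working from Table 3 would apply different SAE criteria to the same laboratory values. Whether an event is a study-specific liver SAE could then depend on the laboratory rather than on the patient. SAP section 2.11, Table 74, counts patients with at least one SAE and does not separate the two rules.

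**Working it through.** No sample size or error rate is involved. The check is to apply the stated criteria to every combination of inputs and see whether one row results.

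**Step 1: is the table complete when the fraction is known?** The bilirubin condition in rows B and C is TB <2.0 or direct <=35%. Its negation is TB >=2.0 and direct >35%, which is row D's condition. So with a known fraction and ALT >3 x ULN, exactly one of B, C or D applies.

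**Step 2: what happens when the fraction is unknown?** (ALT and TB in multiples of ULN)

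| ALT | TB | Hypersensitivity | Direct fraction | Row |
|---|---|---|---|---|
| >3 to 8 | <2.0 | no | any or unknown | B |
| >3 to 8 | >=2.0 | no | <=35% | B |
| >3 to 8 | >=2.0 | no | >35% | D |
| >3 to 8 | >=2.0 | no | **unknown** | **B or D** |
| >8 | <2.0 | no | any or unknown | C |
| >8 | >=2.0 | no | <=35% | C |
| >8 | >=2.0 | no | >35% | D |
| >8 | >=2.0 | no | **unknown** | **C or D** |
| >3 | any | yes | any or unknown | D |

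Enumerating ALT of 5 and 10, TB from 1.0 to 3.0 and fractions of 20%, 50% and unknown gives the same result. The only undetermined cells are those with TB >=2.0, no hypersensitivity and an unknown fraction.

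**Step 3: is a direct fraction always requested?** Footnote (a) to Table 3, the chemistry profile in 8.2 and the Annex III liver panel all list total bilirubin, so the direct level is an add-on test. It is conditional on availability in footnote (b), 9.1 and 9.2. It is unconditional above 1.5 x ULN in the isolated-bilirubin row and in Annex III. These statements do not agree.

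**Step 4: do the SAE rules agree?** (no hypersensitivity, fractionation unavailable)

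| ALT | TB | Liver criteria in 9.1/9.2 | Footnote (b) |
|---|---|---|---|
| 2 | 1.6 to 3.0 | not met | SAE |
| 5 | 1.6 or 1.9 | not met | SAE |
| 5 | 2.0 or 3.0 | cannot be determined | SAE |
| 10 | 1.6 to 3.0 | met | SAE |

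In the last line, the two section 9 criteria complement each other above 8 x ULN, so one of them is met whatever the fraction. The reporting difference is therefore confined to ALT <=8 x ULN. It has two parts: the bilirubin limit (>1.5 against >=2.0 x ULN) and the ALT condition (none against >3 x ULN).

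The first line overlaps the isolated-bilirubin row, which asks for no dose change and notes that pazopanib can raise indirect bilirubin without liver injury. Protocol Table 1 admits patients with total bilirubin up to 1.5 x ULN, so a patient entering at that limit passes the footnote's cut-off with any rise.

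**The case against.** The case for leaving the text alone has several parts.

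- **The patient is not unprotected.** At TB >=2.0 x ULN without a fraction, footnote (b) makes the event an SAE, and 9.2 requires reporting within 24 hours. Section 6.3.1 lets the investigator stop treatment for unacceptable risk. Section 7.6.2 requires full evaluation of liver dysfunction and presents Table 3 as recommendations. This stands and lowers the consequence, but none of it says which row governs.
- **The broader SAE rule may be a deliberate fallback for missing data.** This also stands. Section 9.1 presents its liver list as an addition to the general SAE definition, and an event can be an SAE and still need no dose change. Even so, a deliberate rule should appear in section 9, where reporting staff will look.
- **1.5 x ULN is not a stray number.** Correct. It is the fractionation trigger in the isolated-bilirubin row and Annex III, and a limit in row C's re-challenge list. It does not, however, define the bilirubin elevation in rows B to D or in the section 9 liver SAEs.

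A reader might also infer more than the documents support. One such reading is that any patient with raised ALT and bilirubin fits no row. That is too broad: below 2.0 x ULN row B or C applies without a fraction, and hypersensitivity symptoms with ALT >3 x ULN lead to row D regardless. In the remaining cells the patient is caught between two rows, not outside them all. Another is that fractionation is optional; it is conditional on availability in some places and unconditional in others. A third is that the stop rule is known to fail at some sites. Neither the Protocol (10 sites) nor the SAP (16 sites) says that any site lacks the test.

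**Conclusion.** The point holds in a bounded form. Table 3 leaves the row undetermined for ALT >3 x ULN, total bilirubin >=2.0 x ULN, no hypersensitivity symptoms and an unknown direct fraction. For ALT >3 to 8 x ULN the alternatives are continuing and discontinuing. Above 8 x ULN both candidate rows halt the drug, and the difference is interruption with possible re-challenge against discontinuation.

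Separately, the fractionation requirement is stated in two incompatible ways, and footnote (b)'s SAE rule is missing from 9.1 and 9.2. That second mismatch matters only for ALT <=8 x ULN with total bilirubin >1.5 x ULN and no fraction available.

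The number of patients affected cannot be estimated, since the availability of the test is not documented; if every site can fractionate and does so promptly, it could be none. The conclusion rests on reading the row criteria literally and on footnote (b) applying wherever its mark appears, including the isolated-bilirubin row. No efficacy endpoint is involved. It is still more than a missing detail, because the text gives different stopping or reporting instructions for the same patient depending on which part is followed.

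**What to change.** The sponsor's safety team should reconcile Table 3 with its footnotes, sections 9.1 and 9.2, and Annex III, Table 6, footnote b, so that:

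1. Table 3 names the governing row when ALT is >3 x ULN, total bilirubin is >=2.0 x ULN, hypersensitivity symptoms are absent and the direct fraction is unknown.
2. The fractionation requirement, including whether it depends on availability, reads the same everywhere.
3. The liver SAE criterion is identical in Table 3, 9.1 and 9.2, and states whether footnote (b) applies when ALT is not raised.

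Which row, threshold or action to adopt is for the safety team; none is proposed here. The cost is an amendment to the wording of one table with its footnotes, two SAE lists and one annex footnote. No test is added beyond what Annex III already requests.

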### 7.6.3 Dose Modifications and Management of Diarrhea, Nausea, and Vomiting

These general guidelines are provided to facilitate subject care in the event of diarrhea, thereby avoiding serious complications. Guidelines such as these should never replace sound clinical judgment. Experience thus far suggests that use of monotherapy Pazopanib is associated with an increased incidence of diarrhea, primarily of Grade 1 or 2. In rare cases, diarrhea can be debilitating and potentially life threatening, with dehydration, renal insufficiency, and electrolyte imbalances.

Standardized and universal guidelines have been developed by an American Society of Clinical Oncology panel for treating chemotherapy-induced diarrhea.

Early identification and intervention is critical for the optimal management of diarrhea. A subject's baseline bowel patterns should be established so that changes in patterns while on treatment can be identified. An assessment of frequency, consistency, and duration of diarrhea, as well as knowledge of other symptoms such as fever, cramping, abdominal pain, nausea, vomiting, dizziness and thirst should be taken at baseline, permitting identification of patients at high risk of diarrhea. Patients should be educated on signs and symptoms of diarrhea with instructions to report any changes in bowel patterns to the study site physician.

The NCI CTCAE Version 4.0 criteria for defining diarrhea are provided below.

**Table 4: NCI CTCAE Version 4.0 criteria for defining diarrhea**

Toxicity Grade	Diarrhea (includes diarrhea of small bowel or colonic origin and/or ostomy diarrhea)
1	Increase of <4 stools/day over baseline; mild increase in ostomy output compared to baseline

2	Increase of 4-6 stools/day over baseline; moderate increase in ostomy output compared to baseline
3	Increase of $\geq 7$ stools/day over baseline; incontinence; hospitalization indicated; severe increase in ostomy output compared to baseline; limiting self-care activities of daily living
4	Life threatening consequences, urgent intervention indicated
5	Death

Uncomplicated diarrhea is considered mild to moderate and is defined as CTCAE Grade 1 to 2 with no complicating signs or symptoms.

Complicated diarrhea is severe and defined as CTCAE Grade 3 or 4 or Grade 1 or 2 with one or more of the following signs or symptoms: severe cramping,  $\geq$  Grade 2 nausea/vomiting, decreased performance status, fever, sepsis, Grade 3 or 4 neutropenia, obvious bleeding, dehydration.

### **Management Guidelines**

#### **Uncomplicated diarrhea of CTCAE Grade 1 or 2:**

- Hydration: have subject drink 8 to 10 large glasses (approximately 2 litres) of clear non-caffeinated liquids a day (e.g., broth or electrolyte-containing sports drinks).
- If Grade 2 diarrhea, consider dose reduction of investigational products.
- Dietary modifications: have subject stop all lactose-containing products and eat frequent, small meals
- Pharmacologic intervention using loperamide:
  - Begin loperamide at initial dose of 4 mg followed by 2 mg every 4 hours or after every unformed stool. The recommended maximum daily dose of loperamide is 16 mg/day.
  - Continuation of loperamide is suggested until diarrhea-free for 12 hours.
  - If mild to moderate diarrhea persists for more than 24 hours, administer loperamide 2 mg every 2 hours and pursue evaluation for other treatable causes.
  - If mild to moderate diarrhea persists after 48 hours total treatment with loperamide, discontinue study drug(s) and consider initiation of second-line agents (lomotil, octreotide).

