#### **Complicated diarrhea of CTCAE Grade 3 or 4 diarrhea or Grade 1 or 2 with complicating features requires aggressive management:**

- Subject must call study site physician immediately in response to any event of severe diarrhea with or without complications as listed above.
  - Hospitalization may be required for subjects most at risk for life-threatening complications.
- Interrupt investigational products until symptoms resolve; consider reintroducing at a reduced dose (discuss with Chief Trial Investigator or designee).
- If loperamide has not been initiated, begin loperamide usage immediately at an initial dose of 4 mg followed by 2 mg every 2 hours or after every unformed stool. The recommended maximum daily dose of loperamide is 16 mg/day.

- If no improvement in severity after 24-hours of maximal loperamide dosing, subject must visit study site and be evaluated:
  - For dehydration, use intravenous fluids as appropriate.
- Antibiotic therapy should be considered in patients, who present with signs and symptoms of bacterial diarrhea such as fever, bloody diarrhea, and presence of fecal leukocytes. Investigators should have a low threshold to start such treatment in patients with Grade 3 or Grade 4 neutropenia.
- Before initiation of antimicrobial therapy, stool cultures should be obtained. When bacterial etiology for diarrhea is suspected, study-treatment and anti-motility agents (loperamide or others) should be held.
- Intervention should be continued until diarrhea free for 24 hours.

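### The two every-2-hours loperamide schedules in Protocol 7.6.3 exceed the section's own 16 mg/day maximum if followed by the clock for 24 hours, and the text does not say how the maximum applies.

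*Protocol*

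**What the plan says.** Protocol 7.6.3 (Management Guidelines) gives three loperamide schedules and states one daily maximum twice.

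- **Uncomplicated diarrhea, start:** "Begin loperamide at initial dose of 4 mg followed by 2 mg every 4 hours or after every unformed stool". The maximum follows at once: "The recommended maximum daily dose of loperamide is 16 mg/day".
- **Uncomplicated diarrhea, escalation:** once it has lasted more than 24 hours, "administer loperamide 2 mg every 2 hours and pursue evaluation for other treatable causes". This line has no stool-based alternative and does not mention the maximum. The next step begins: "If mild to moderate diarrhea persists after 48 hours total treatment with loperamide". At that point the study drug is to be discontinued and second-line agents considered.
- **Complicated diarrhea:** if loperamide has not been started, "begin loperamide usage immediately at an initial dose of 4 mg followed by 2 mg every 2 hours or after every unformed stool". The 16 mg/day maximum is repeated in the next sentence. The following bullet requires a site visit and evaluation if severity has not improved after a day of loperamide at its maximal level.

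The introduction to 7.6.3 says that pazopanib monotherapy is associated with more diarrhea, mainly Grade 1 or 2. It also says that these are general guidelines and do not replace clinical judgment.

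**The concern.** A fixed dose at a fixed interval implies a daily total. For both 2-hourly schedules that total is above the maximum printed in the same section. The text does not say that dosing stops once 16 mg is reached, does not limit it to waking hours, and does not lift the maximum for these steps. A site therefore has to decide for itself which figure governs.

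The stake is patient safety and uniform management of an adverse event that the protocol itself links to the study drug. Two later decisions in the section also build on these steps. The evaluation visit for complicated diarrhea depends on a day of maximal loperamide, which could mean 16 mg/day or the full 2-hourly schedule. In uncomplicated diarrhea, stopping the study drug depends on persistence after 48 hours of loperamide, and the second of those two days is the escalation step.

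**Working it through.** **Inputs, all from Protocol 7.6.3**

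- Stated maximum: 16 mg/day, given under both uncomplicated and complicated diarrhea.
- Uncomplicated, start: 4 mg, then 2 mg every 4 hours or by stool.
- Uncomplicated, beyond 24 hours: 2 mg every 2 hours, with no alternative.
- Complicated: 4 mg, then 2 mg every 2 hours or by stool.
- Duration of the uncomplicated 2-hourly step: from 24 to 48 hours of total loperamide treatment, about one full day.

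**Formula**

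Total over 24 hours = first dose + 2 mg x (number of further doses at the stated interval). The main count starts at hour 0 and leaves out the dose at hour 24. The variant counts that dose too.

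**Results by the clock**

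| Schedule | Calculation | Total | Share of 16 mg | With hour-24 dose |
|---|---|---|---|---|
| Uncomplicated, start (every 4 h) | 4 + 5 x 2 | 14 mg | 88% | 16 mg |
| Uncomplicated, beyond 24 h (every 2 h) | 12 x 2 | 24 mg | 150% | 26 mg |
| Complicated, clock branch, first 24 h (every 2 h) | 4 + 11 x 2 | 26 mg | 163% | 28 mg |

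The 16 mg/day figure is a stated limit, not a derived one. The starting schedule agrees with it: 14 mg, or exactly 16 mg with the hour-24 dose, and 12 mg/day thereafter. The two 2-hourly schedules do not agree with it. The excess is 24 - 16 = 8 mg in the first case and 26 - 16 = 10 mg in the second. If the complicated schedule continues, each later day is 12 x 2 = 24 mg.

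**If 16 mg is read as a hard ceiling**

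- Uncomplicated 2-hourly step: 16 / 2 = 8 doses. The eighth falls at hour 14, and 12 - 8 = 4 scheduled doses are dropped.
- Complicated, clock branch: 4 + 6 x 2 = 16 mg. This is reached with the seventh dose, at hour 12, and 12 - 7 = 5 scheduled doses are dropped.

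**If dosing is limited to 16 waking hours (an assumption; the protocol does not say this)**

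- Uncomplicated 2-hourly step: 8 x 2 = 16 mg, or 18 mg with the hour-16 dose.
- Complicated, clock branch: 4 + 7 x 2 = 18 mg, or 20 mg with the hour-16 dose.

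Under this assumption the uncomplicated step just meets the maximum or slightly exceeds it, and the complicated clock branch still exceeds it.

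**The case against.** The strongest reply is that a stated maximum is ordinarily a ceiling on whatever schedule it accompanies: dose at the interval until the maximum is reached, then stop. In the complicated-diarrhea bullet the maximum is the very next sentence, and the reference to maximal dosing in the following bullet suggests that the authors treat it as an operating limit. In the uncomplicated list it sits two lines above the escalation step, under the same loperamide bullet, and is worded for the drug as a whole. The maximum is only recommended, the section calls itself general guidance, and the uncomplicated 2-hourly step lasts about a day.

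Much of this stands, and it rules out some stronger readings:

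- A reader might infer that sites cannot comply with both figures. The documents do not support that, because a site that applies the ceiling can.
- A reader might infer that every loperamide schedule breaks the maximum. The starting 4-hourly schedule does not by the clock.
- A reader might take 26 mg as what the complicated schedule always delivers. It is the clock branch only; dosing by stool depends on stool count.

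The reply does not remove the mismatch. Under the ceiling reading, a third or more of the scheduled 2-hourly doses are dropped (4 of 12 and 5 of 12), and no line says so. The escalation line raises the frequency without mentioning the maximum, so it can be read either as still capped or as replacing the cap.

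**Conclusion.** The inconsistency is real and limited to the two 2-hourly schedules. Followed by the clock for 24 hours, they total 24 mg and 26 mg against a stated 16 mg/day, which is 150% and 163% of the maximum. The uncomplicated escalation step is the clearer case, because it has no stool-based alternative and runs for about a full day. The complicated schedule conflicts on its clock branch.

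The result assumes dosing around the clock, which is how the intervals are written, and leaves out the hour-24 dose. Counting that dose raises the totals to 26 and 28 mg. An unstated waking-hours limit would lower them to 16 to 18 mg and 18 to 20 mg.

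The fault is that the text does not say how the maximum applies, which also leaves unclear what counts as a day of maximal loperamide. A reader might infer from this a weakness in the trial's statistical design. There is none here: the pazopanib starting dose, the primary endpoint definition, the decision rules and the error rates are unaffected.

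**What to change.** The sponsor's clinical team should reconcile the two 2-hourly schedule lines with the 16 mg/day maximum, under both uncomplicated and complicated diarrhea, so that one consistent set of figures applies. The revised text should say expressly whether the maximum limits these steps, and what a day of maximal loperamide means for the evaluation visit. Which figure should govern is a clinical decision, and no dose is proposed here.

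The cost is protocol wording in 7.6.3. No analysis, sample-size or SAP change follows from it.
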